5.10 Beginning and End of the Trial

The overall trial begins when the first subject signs the informed consent form. The overall trial ends when the last subject completes the last study-related phone-call or visit, discontinues from the trial or is lost to follow-up (i.e. the subject is unable to be contacted by the investigator).

5.11 Clinical Criteria for Early Trial Termination

There are no pre-specified criteria for terminating the trial early.

6.0 TRIAL FLOW CHART

The Trial Flow Chart for this study has been split into two parts:

Part 1: Screening and POS IV solution treatment phase of the study (Visits 1-14)

Part 2: POS PFS and Follow-up Phases of the study (Visits 15-28)

6.1 PART 1: (Visits 1-14) SCREENING, BASELINE & POS IV SOLUTION VISITS

Visit Number	POS IV SOLUTION TREATMENT PHASE														Last Day of POS IV Solution ^a
	1	2	3	4	5	6	7	8	9	10	11	12	13	14	
Visit Title:	Screening	Baseline	Day 1	Day 2	Day 3	Day 4	Day 5	Day 6	Day 7	Day 8	Day 9	Day 10	Optional Use of POS IV Solution Day 11-28	Day 10	
Scheduling window	Day -7 to < Day -1	Day-1													
Administrative Procedures															
Obtain Informed Consent/Assent	X														
Informed Consent for Future Biomedical Research (optional)	X														
Review Inclusion/Exclusion Criteria	X	X													
Issue Subject Identification Card	X														
Medical History	X														
Prior/Concomitant Medications	X	X	X	X	X	X	X	X	X	X	X	X	X	X	
Screening Number Assignment	X														
Randomization Number Assignment			X												
Clinical Procedures/Assessments															
Complete physical examination	X	X													
Focused physical examination ^b			X		X	X	X	X	X	X	X	X ^b	X		
Body Weight (kg)	X	X													
Height (cm)	X														
Vital Signs	X	X	X	X	X	X	X	X	X	X	X	X	X	X	
Electrocardiogram ^c		X													
Chest Radiograph ^d		X													
IV Study Drug Administration			X	X	X	X	X	X	X	X	X	X	X	X	
Adverse Event Monitoring		X	X	X	X	X	X	X	X	X	X	X	X	X	

Visit Number	1	2	POS IV SOLUTION TREATMENT PHASE												
			3	4	5	6	7	8	9	10	11	12	13	14	
Visit Title:	Screening	Baseline	Day 1	Day 2	Day 3	Day 4	Day 5	Day 6	Day 7	Day 8	Day 9	Day 10	Optional Use of POS IV Solution Day 11-28	Last Day of POS IV Solution ^a	
Scheduling window	Day -7 to < Day -1	Day-1													
Laboratory Procedures/Assessments															
Pregnancy Test (Serum) ^e	X	X													
Hematology/Serum Chemistry ^{f,g}	X	X ^f			X ^g			X ^g				X ^g	X ^g	X	
Absolute Neutrophil Count ^h	X	X ^h			X ^h			X ^h				X ^h	X ^h	X	
POS PK Trough Sampling ^{i,j}								X ⁱ					X ^j		
POS Full PK Sampling ^k									X ^k						
Cyclodextrin (SBE β CD) PK sampling ^l									X ^l						
DNA/Buccal swab for Future Biomedical Research (optional) ^m			X												

- a. The last day of POS IV solution can occur anytime between the 10th and the 18 day of treatment with POS IV solution.
- b. After Day 1, the focused physical exam should be performed 3 times per week until the last day of POS IV
- c. ECG may be performed on Day 6, 7, or 8
- d. As clinically indicated to rule out fungal infection.
- e. Pregnancy test will be done on females of childbearing potential. If a serum pregnancy test is performed at screening and the baseline visit occurs more than 2 days after screening, the serum pregnancy test should be repeated at the baseline visit. If the baseline visit occurs 2 days or less from the screening visit, serum pregnancy test is sufficient and a pregnancy test does not need to be repeated at the baseline visit. A urine pregnancy test may be substituted for a serum pregnancy test at the screening visit; however, if a urine pregnancy test is used for screening, it must be followed up with a confirmed negative serum pregnancy test within 48 hours.
- f. Hematology: complete blood count (CBC) with differential; serum chemistry: BUN, calcium, serum creatinine, potassium, sodium, glucose, AST, ALT, alkaline phosphatase, total bilirubin, albumin, total protein, magnesium, chloride, and bicarbonate. At Baseline, only repeat hematology, chemistry & ANC if > 2 days since screening labs.
- g. Hematology and chemistry testing must be performed 2 times per week with at least 2 days in between samples.
- h. Collect ANC 2 times per week while on POS IV solution with at least 2 days in between samples.
- i. **Plasma TROUGH sampling** (POS only: 0.35 mL of blood per sample) pre-dose (0 hr) on Day 6 of IV treatment. The Day 6 sample may be collected on Day 5 to coincide with other labs. For premature discontinuations (prior to Day 7), a trough level sample will be taken approximately 24 hours post start of infusion of the last dose, and all other safety assessments will be performed according to the Last Day of POS IV solution schedule.
- j. For subjects continuing POS IV solution beyond Day 10 collect troughs once per week.
- k. **POS PK sampling during POS IV solution administration:** Full PK sampling may be performed on any day from Day 7-10. Perform PK sampling at pre-dose (0 hour), within 15 minutes after the end of infusion, and at approximately 4, 6, 12 and 24 hours post start of infusion.
- l. **Cyclodextrin (SBE β CD) PK sampling during POS IV solution administration**(0.35 mL of blood per sample): PK sampling at pre-dose (0 hour), within 15 minutes after the end of infusion, and at approximately 4, 6 and 12 hours post start of infusion. May be performed on any day from Day 7-10 and should coincide with POS full PK.
- m. Participation in future biomedical research is optional. Informed consent for future biomedical research must be obtained before the DNA Buccal swab samples. The DNA buccal swab should be collected on Day 1 on randomized subjects only or at a later date, as soon as the informed consent is obtained.

6.2 PART 2: (VISITS 15-28) ORAL (PFS) TREATMENT AND FOLLOW-UP VISITS

Visit Number	POS PFS TREATMENT												FOLLOW-UP		
	15	16	17	18	19	20	21	22	23	24	25	26	27	28	
Visit Title:	1st Day of POS PFS ^a	2 nd Day of POS PFS	3 rd Day of POS PFS	4 th Day of POS PFS	5 th Day of POS PFS	6 th Day of POS PFS	7 th Day of POS PFS	8 th Day of POS PFS	9 th Day of POS PFS	10 th Day of POS PFS	Optional POS PFS Day 11-18 ^b	EOT/Last Day of POS PFS ^b	FOLLOW-UP 14 Days after End of Therapy (EOT) (POS IV solution or POS PFS)	Survival Assessment ⁿ	
Scheduling window	Day after last IV Dose												EOT +14 DAYS	Day 90-110	
Administrative Procedures															
Prior/Concomitant Medications	X	X	X	X	X	X	X	X	X	X	X	X	X	X	
Study Medication/Food Diary Assessment ^c	X	X	X	X	X	X	X	X	X	X	X	X	X	X	
Provide or collect Study Medication/Food Diary (outpatients) ^d	X ^d					X ^d				X ^d		X ^d			
Clinical Procedures/Assessments															
Focused physical exam ^e	X		X			X				X	X	X			
Body Weight (kg) ^f	X														
Vital Signs ^e	X		X			X				X	X	X			
Electrocardiogram ^g										X ^g					
Oral Study Drug Administration	X ^a	X	X	X	X	X	X	X	X	X	X	X			
Assessment of Palatability	X				X							X			
Adverse Event Monitoring	X	X	X	X	X	X	X	X	X	X	X	X	X	X	
Survival Assessment ⁿ															X
Laboratory Procedures/Assessments															
Hematology/Serum Chemistry ^{h,i}			X ^{h,i}			X ^{h,i}				X ^{h,i}	X ^{h,i}	X ^{h,i}			
Absolute Neutrophil ^j			X ^j			X ^j		X ^j			X ^j	X			
POS PK Trough Sampling ^{k,l}						X ^k					X ^{k,l}	X ^k			
POS Full PK Sampling ^m										X ^m					

- a. The first day of POS PFS formulation can occur any day after Day 10 of POS IV solution.
- b. The last day of POS PFS can occur anytime between the 10th through the 18th day of POS PFS (combined treatment with POS IV and POS PFS cannot exceed 28 days).
- c. Food information will be collected in study medication diaries for subjects receiving PFS. The timing and characteristics of food taken will be recorded for each dose. Outpatients will maintain the daily dosing record and will record the actual time of dosing at the time of administration and the timing and characteristics of meals.
- d. The SM/Food diary should be provided to outpatients and the completed diaries collected at least once a week at a scheduled outpatient visit.
- e. For inpatients, perform focused physical exam and record vital signs 2 times per week, at least 2 days apart while on POS PFS. For outpatients, perform focused physical exam, and record vital signs once per week while on POS PFS.
- f. The subject's weight as measured within 3 days prior to the first dose of oral treatment (PFS) will be used to calculate the first and all subsequent doses of PFS.
- g. ECG may be performed on Day 8, 9, or 10 of PFS
- h. Hematology: complete blood count (CBC) with differential; Serum Chemistry: BUN, calcium, serum creatinine, potassium, sodium, glucose, AST, ALT, alkaline phosphatase, total bilirubin, albumin, total protein, magnesium, chloride, and bicarbonate. The first sample after the first day of POS PFS should be collected no later than the 5th dose of POS PFS.
- i. For inpatients, hematology and chemistry testing must be performed 2 times per week with at least 2 days in between samples. For outpatients, lab testing must be performed once per week while on POS PFS
- j. ANC must be drawn a minimum of twice a week for inpatients and once per week for outpatients while on POS PFS and during periods of neutropenia (ANC <500/mm³). The first sample after the first day of POS PFS should be collected no later than the 5th dose of POS PFS.
- k. **POS plasma trough sampling** during POS PFS administration (0.35 mL of blood per sample): Collect trough sample pre-dose (0 hr) on the 6th day of POS PFS and at the end of POS therapy. For premature discontinuations, a trough level sample will be taken approximately 24 hours after administration of the last dose, and all other safety assessments will be performed according to the Last Day of POS PFS schedule. The trough may be collected at either the 5th or 6th day of POS PFS to coincide with other labs.
- l. For subjects continuing for more than 7 days of POS PFS treatment, POS trough samples should be collected once per week with other required labs.
- m. **PK full sampling during POS PFS administration** (0.35 mL of blood per sample): If an inpatient, perform PK sampling at pre-dose (0 hour), and 2, 4, 6, 8, and 24 hours post-dose; if an outpatient, perform PK sampling at predose (0 hour) 2, and 4 hours post-dose. Full PK sampling may be performed anytime between the 7th through the 10th day of POS PFS treatment.
- n. Survival Assessment, if the subject is alive or dead, will be recorded on the electronic case report form (eCRF). If the subject dies, the cause and date of death will be recorded. This assessment can be made by telephone or by medical records.

7.0 TRIAL PROCEDURES

7.1 Trial Procedures

The Trial Flow Chart - Section 6.0 summarizes the trial procedures to be performed at each visit. Individual trial procedures are described in detail below. It may be necessary to perform these procedures at unscheduled time points if deemed clinically necessary by the investigator.

Furthermore, additional evaluations/testing may be deemed necessary by the investigator and or the Sponsor for reasons related to subject safety. In some cases, such evaluation/testing may be potentially sensitive in nature (e.g., HIV, Hepatitis C, etc.), and thus local regulations may require that additional informed consent be obtained from the subject. In these cases, such evaluations/testing will be performed in accordance with those regulations.

7.1.1 Administrative Procedures

7.1.1.1 Informed Consent

The investigator or qualified designee must obtain documented consent from each potential subject or each subject's legally acceptable representative prior to participating in a clinical trial or Future Biomedical Research.

7.1.1.1.1 General Informed Consent

Consent must be documented by the subject's dated signature or by the subject's legally acceptable representative's dated signature on a consent form along with the dated signature of the person conducting the consent discussion.

A copy of the signed and dated consent form should be given to the subject before participation in the trial.

The initial informed consent form, any subsequent revised written informed consent form and any written information provided to the subject must receive the IRB/ERC's approval/favorable opinion in advance of use. The subject or his/her legally acceptable representative should be informed in a timely manner if new information becomes available that may be relevant to the subject's willingness to continue participation in the trial. The communication of this information will be provided and documented via a revised consent form or addendum to the original consent form that captures the subject's dated signature or by the subject's legally acceptable representative's dated signature.

Specifics about a trial and the trial population will be added to the consent form template at the protocol level.

The informed consent will adhere to IRB/ERC requirements, applicable laws and regulations and Sponsor requirements.

7.1.1.1.2 Consent and Collection of Specimens for Future Biomedical Research

The investigator or qualified designee will explain the Future Biomedical Research consent to the subject, answer all of his/her questions, and obtain written informed consent before performing any procedure related to the Future Biomedical Research sub-trial. A copy of the informed consent will be given to the subject.

7.1.1.2 Inclusion/Exclusion Criteria

All inclusion and exclusion criteria will be reviewed by the investigator or qualified designee to ensure that the subject qualifies for the study.

7.1.1.3 Subject Identification Card

All subjects will be given a Subject Identification Card identifying them as participants in a research trial. The card will contain trial site contact information (including direct telephone numbers) to be utilized in the event of an emergency. The investigator or qualified designee will provide the subject with a Subject Identification Card immediately after the subject provides written informed consent.

7.1.1.4 Medical History

A detailed medical history will be obtained by the investigator or qualified designee and recorded in the eCRF. The medical/disease history should include:

- Identify the specific medical condition listed in Inclusion criteria #3 that qualified the subject for the study
- Details regarding any ongoing or prior cancer diagnoses, immunosuppressive conditions (including HIV), and transplant procedures (BMT and solid organ)
- Details of previous surgeries or trauma
- Details of previous arrhythmias
- Details regarding recent or ongoing bacterial infections
- Detail of any prior history of fungal infection
- Any history of hepatitis
- Any significant signs or symptoms related to underlying medical conditions
- Results of any abnormal chemistry, hematology lab or imaging results performed within 7 days of starting the trial.

Any medical conditions found at the Screening and Baseline exams will be recorded on the eCRF in the Medical History module. The status of the condition will be evaluated as “resolved”, “stable” or “unstable”. Any unstable medical condition will require a comment.

7.1.1.5 Prior and Concomitant Medications Review

7.1.1.5.1 Prior Medications

The investigator or qualified designee will review prior medication use, including any protocol-specified washout requirements, and prohibited medications for the 14 days prior to initiation of POS treatment as outlined in Section 5.5.1 and listed in [Table 6](#).

- Record prior medication (prescription or over the counter) taken by the subject within 14 days before starting the trial. It is important to also record any protocol-specified prohibited medications, as outlined in Section 5.5.1 ([Table 6](#)), received during the 14-day period prior to enrollment.
- The identity of the therapy, the dates started and stopped (or notation of “continuing” if that is the case), and the reason for use must be recorded for all medications.
- Patients receiving other systemic antifungal agents (IV, oral or nasal/inhaled) as prophylactic therapy must discontinue these treatments prior to study drug administration. No other systemic antifungal agents may be administered during the study treatment phase (i.e., POS IV solution/PFS) without sponsor approval.

7.1.1.5.2 Concomitant Medications

The investigator or qualified designee will record all medications and therapeutic procedures taken by the subject during POS treatment and for the 14 days of safety follow-up. Of note, any protocol-specified prohibited medications (see Section 5.5.1 and [Table 6](#)) received during the 14-day follow-up period after POS had ended should also be recorded.

- Parenteral nutrition products should be recorded as concomitant medication.

The identity of the therapy, the dates started and stopped (or notation of “continuing” if that is the case), and the reason for use must be recorded for all medications. The use of any concomitant medication must relate to an AE or the subject’s medical history.

7.1.1.6 Assignment of Screening Number

All consented subjects will be given a unique screening number that will be used to identify the subject for all procedures that occur prior to randomization or allocation. Each subject will be assigned only one screening number. Screening numbers must not be re-used for different subjects.

Any subject who is screened multiple times will retain the original screening number assigned at the initial screening visit.

Specific details on the screening visit requirements (screening/rescreening) are provided in Section 7.1.5.1.

7.1.1.7 Assignment of Randomization Number

All eligible subjects will receive a randomization number. The randomization number identifies the subject for all procedures occurring after randomization. Once a randomization number is assigned to a subject, it can never be re-assigned to another subject.

A single subject cannot be assigned more than 1 randomization number.

7.1.1.8 Trial Compliance (Medication)

Study medication compliance will be monitored by ongoing data review during the IV treatment phase (POS IV solution) of the study. Compliance during the oral treatment phase (POS PFS) will be verified by review of the study medication/food diary.

Interruptions from the protocol specified treatment (defined as missing one or more doses) require consultation between the investigator and the Sponsor and written documentation of the collaborative decision on subject management.

The shifting of the timing of a dose (within the window provided to accommodate a subject's schedule) is not considered an interruption.

7.1.2 Clinical Procedures/Assessments

7.1.2.1 Physical Examination

The principal investigator or designee will perform a complete physical exam at the Screening & Baseline Visits and will perform directed (focused) physical exams at least two times a week thereafter as indicated in the Trial Flow Chart (Section 6.0). Any medical conditions found at the Screening and Baseline exams will be recorded on the eCRF in the Medical History module. The status of the condition will be evaluated as "resolved", "stable" or "unstable". Any unstable medical condition will require a comment. An exacerbation of a pre-existing condition or any new finding that occurs during the study will be captured as an adverse event and recorded in the Adverse Event module of the eCRF.

7.1.2.2 Body Weight (kg)

Body weight at Baseline will be used to calculate the subject's dose for the IV treatment phase of the study. The subject's weight measured within three days prior to the first dose of oral treatment should be used to calculate all oral treatment (PFS) doses. The actual weight measured should be recorded. Body weight should be obtained without shoes. At each required visit, it is preferred that the weight should be measured on the same scale for the same individual. Measurements should be recorded to the nearest tenth of a kg.

7.1.2.3 Height (cm)

Height measurements should be taken without shoes and be recorded to the nearest cm.

7.1.2.4 Vital Signs

The pretreatment vital signs will be considered the Baseline values.

Vital signs will be obtained by the principal investigator or designee. Systolic and diastolic blood pressure (mm Hg), heart rate (bpm) and body temperature (°C or °F) will be obtained according to the local standard procedure and will be recorded.

If the scheduled time for vital sign measurements coincides with a blood collection, the vital signs should be performed prior to the blood collection or at least 5 minutes afterwards. The same timing for obtaining the vital signs (before or after blood collection) should be used for all vital sign measurements.

Body temperatures obtained within one hour of blood product transfusions should not be included on the eCRF. On the required days, the maximum daily temperature (outside of blood transfusions) will be collected and recorded on the eCRF.

7.1.2.5 Electrocardiogram

Two baseline ECGs must be performed at least 5 minutes apart at the Baseline Visit for purposes of protocol eligibility.

Prior to study drug administration, all ECGs should be reviewed for clinically significant abnormalities and reported as normal (or with findings that are not clinically significant).

ECGs should also be performed on Day 6, 7 or 8 of POS IV solution treatment and on Day 8, 9, or 10 of POS PFS treatment and as clinically indicated for the evaluation of AEs.

ECGs performed after the Baseline Visit should be done at approximately the same time of day (AM or PM) that baseline ECGs were performed.

A standard 12-lead ECG, reporting ventricular rate, PR, QRS, QT, and QTc intervals, will be performed. Any clinically significant abnormality must be followed until stabilization or return to baseline.

Any change in the QTc interval of greater than 30 msec post Baseline (when compared to Baseline) will require a repeat ECG, and a determination of serum potassium (K), calcium (Ca), magnesium (Mg), and electrolyte replacement, if necessary. Additional evaluation may be required, and the principal investigator should determine if discontinuation of study drug or other evaluation is required in consultation with the project physician.

If the QTc interval change from Baseline is greater than 60 msec, study drug should be interrupted while evaluation and treatment of other etiologies is ongoing (Section 5.8, Subject Discontinuation Criteria).

During the Treatment Phase, if a QTc interval is found to be abnormal (symptomatic QTc intervals greater than 450 msec [males] or 470 msec [females]) after repeated ECG for

confirmation a cardiology consultation is to be requested to determine possible etiologies in addition to or other than study drug should also be performed at the same time (e.g., review of other concomitant drugs, and determination of serum Mg, Ca, and K levels). The investigator will determine if discontinuation of study drug is warranted after clinical examination of the subject and pertinent laboratory evaluation, and discussion of the case with the Sponsor's project physician.

ECGs performed will be transferred to a blinded third party for an evaluation of QT, QTc (Fredericia and Bazett), PR, and QRS intervals and ventricular rate, as well as an overall clinical interpretation. The final results of the third-party analysis will be considered the definitive ECG data and will be the only ECG data used in the analysis.

Note: When the collection of vital signs, ECGs, and PK samples coincide, the blood samples for PK determination should be collected first (so that the PK samples are collected on time), followed by the vital signs, and then the ECG. It is preferred that the ECG be performed at the same time each day (e.g., morning) to reduce diurnal variation.

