5.8 Subject Withdrawal/Discontinuation Criteria

Subjects may withdraw consent at any time for any reason or be dropped from the trial at the discretion of the investigator should any untoward effect occur. In addition, a subject may be withdrawn by the investigator or the Sponsor if enrollment into the trial is inappropriate, the trial plan is violated, or for administrative and/or other safety reasons. Specific details regarding discontinuation or withdrawal procedures; including specific details regarding withdrawal from Future Biomedical Research, are provided in Section 7.1.4 – Other Procedures.

A subject must be discontinued from the trial for any of the following reasons:

- The subject or legal representative (such as a parent or legal guardian) withdraws consent.
- Death;

In this trial, a subject may discontinue from treatment, but continue to participate in the regularly scheduled activities of the study as long as the subject does not withdraw consent.

A subject must be discontinued from treatment (but may continue to be monitored in the trial) for any of the following reasons:

- Serious adverse experience related to study therapy or the occurrence of an adverse experience (clinical or laboratory) that, in the judgment of the investigator, warrants withdrawal of study therapy;
- Failure to comply with the dosing, evaluations, or other requirements of the study;
- Request of the subject or subject's parent or legally authorized representative (subjects have the right to discontinue treatment or the study at any time for any reason);
- The subject has a confirmed positive serum pregnancy test;
- Initiation of other systemic (IV, oral, or nasal/inhaled) antifungal agents for empiric, pre-emptive or definitive therapy of IFI, including agents containing amphotericin B

(AMB), echinocandins, azole and triazole antifungal agents, or other investigational antifungal drugs;

- Subjects who, following Baseline require any of the prohibited medications listed in [Table 6](#) of Section 5.5.1;
- Any situation or condition which may threaten the subject's health or well-being by continuing on study treatment;
- Administrative (e.g. study termination);

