- An AST or ALT value that is greater than or equal to 3 X the ULN and an elevated total bilirubin value that is greater than or equal to 2 X the ULN and, at the same time, an alkaline phosphatase value that is less than 2 X the ULN, as determined by way of protocol-specified laboratory testing or unscheduled laboratory testing. **NOTE:** Patients will be discontinued from study therapy but followed for safety until the abnormal value(s) has/have normalized, stabilized, or returned to baseline;
- If the QTc interval change from Baseline is greater than 60 msec or the QTc interval is ≥ 500 msec (refer to Section 7.1.2.5 for details on ECG testing).

A subject who develops a superficial fungal infection (e.g., cutaneous fungal infection, thrush or candidal vaginitis) may be treated with topical antifungal agents (nystatin and/or azole formulations) and continued on study drug if in the judgment of the investigator there is no evidence of systemic involvement or more extensive mucosal involvement that would require more specific systemic antifungal therapy. Superficial candidiasis (including signs and symptoms and supportive laboratory findings) must be noted on the eCRF. It is the right and duty of the investigator or subinvestigator to interrupt treatment of any subject if he/she feels that study discontinuation is necessary to protect the subject, or that there are unmanageable factors, that may interfere significantly with the study procedures or interpretation of the results.

If a subject discontinues prior to completion of the study, the reason for the discontinuation will be obtained. The date of the last dose of study medication and the date of the last assessment and/or contact will be obtained. This information will be documented in the appropriate section of the eCRF. A follow-up contact (telephone or visit) will be arranged as appropriate.

At the time of discontinuation, every effort should be made to ensure all procedures and evaluations scheduled for the final study visit are performed (see Section 6.0, Trial Flow Chart). For all discontinued subjects, a trough sample should be collected within 24 hours of the last dose, AEs should be recorded and followed to outcome and medication compliance should be assessed.

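### For a QTc change above 60 msec, Section 5.8 requires discontinuation while Section 7.1.2.5 describes only an interruption, so it is unclear whether dosing may resume

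*Combined protocol and SAP*

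**What the plan says.** Section 5.8 (Subject Withdrawal/Discontinuation Criteria) opens its list of treatment-stopping events with "A subject must be discontinued from treatment (but may continue to be monitored in the trial) for any of the following reasons". The last bullet reads "If the QTc interval change from Baseline is greater than 60 msec or the QTc interval is ≥ 500 msec". It carries no exception for another cause or for recovery, and it points elsewhere only in the words "refer to Section 7.1.2.5 for details on ECG testing".

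Section 7.1.2.5 (Electrocardiogram) sets out steps for on-treatment QTc findings:

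- **Change above 30 msec:** repeat ECG, electrolytes, and then "the principal investigator should determine if discontinuation of study drug or other evaluation is required in consultation with the project physician".
- **Change above 60 msec:** "study drug should be interrupted while evaluation and treatment of other etiologies is ongoing", with a bracketed reference to Section 5.8 by its title as the discontinuation criteria.
- **Symptomatic QTc above 450 msec (males) or 470 msec (females), on repeat ECG:** cardiology consultation, review of other causes, and then "The investigator will determine if discontinuation of study drug is warranted after clinical examination of the subject", with discussion with the Sponsor's project physician.

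Section 7.1.1.8 governs missed doses: "Interruptions from the protocol specified treatment (defined as missing one or more doses) require consultation between the investigator and the Sponsor", with the joint decision documented in writing. Table 9 (Rechallenge) adds that the Sponsor's clinical director must approve in advance a rechallenge after a serious and possibly drug-caused event, or any re-exposure carrying significant added risk.

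**The concern.** A stopping rule should lead two sites to the same action on the same ECG. Here a site working from Section 5.8 ends treatment. A site working from Section 7.1.2.5 holds drug, looks for another cause, and may then ask whether to restart. The situation is realistic: Section 5.5.3 allows several drugs with a torsades risk alongside posaconazole, with monitoring, so another explanation for a prolonged QTc will sometimes be at hand.

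At stake is re-exposure of a child to study drug after a large QTc change, decided between site and Sponsor with no criterion in the protocol. A restart would also be a deviation from Section 5.8, even though the site could believe it was following Section 7.1.2.5.

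**Working it through.** The plan gives no figure to reproduce. The check is a side-by-side reading, with small arithmetic examples for the boundaries.

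**1. Same trigger, different action**

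| | Section 5.8 | Section 7.1.2.5 |
|---|---|---|
| Trigger | QTc change from Baseline above 60 msec | QTc change from Baseline above 60 msec |
| Force | must | should |
| Action | discontinue from treatment | interrupt |
| Duration | no end stated | while other causes are being worked up and treated |
| Immediate effect | drug stops | drug stops |
| Restart | not allowed for | implied, not stated |

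**2. Does interruption mean discontinuation here?** Section 7.1.1.8 defines an interruption as one or more missed doses, followed by a management decision, which is not in itself a discontinuation. Section 5.8 does once use the verb interrupt loosely beside study discontinuation, but in a general sentence on investigator judgment and not in the QTc rule. The hepatic bullet in the same list shows what a clear rule looks like: it says that therapy is discontinued and that follow-up continues until the values settle.

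**3. Do the cross-references settle it?** Section 5.8 refers to 7.1.2.5 for ECG testing only. Section 7.1.2.5 names 5.8 but does not say that the hold must become a discontinuation. Neither gives precedence.

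**4. Who decides on restart, and by what rule?** Section 7.1.1.8 supplies a process (Sponsor consultation and a written decision) but no QTc criterion. Table 9 supplies an approval step where it applies and refers to dose modification guidelines in the protocol. Section 5.2.1, which carries that subject in its title, covers only dose calculation and cohort escalation.

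**5. Boundary examples (hypothetical male subjects)**

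- 390 to 455 msec: 455 − 390 = 65, above 60. Section 5.8: discontinue. Section 7.1.2.5: interrupt and, if symptomatic, the investigator also decides on discontinuation.
- 445 to 500 msec: 500 − 445 = 55, not above 60, but QTc is at 500. Section 5.8: discontinue. Section 7.1.2.5 does not mention the 500 msec stop on treatment, but does not cancel it.
- 420 to 460 msec, symptomatic: 460 − 420 = 40, and QTc is below 500. Neither 5.8 criterion is met, so investigator judgment is the right rule.

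Only the change above 60 msec has two differently worded actions tied to one trigger.

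**The case against.** The strongest reply is that the sections can be read together: hold drug, work up the cause, then apply Section 5.8, which 7.1.2.5 cites by name. No sentence permits a restart, and an unconditional must should prevail over silence. The work-up would still have a purpose after a permanent stop, because 7.1.2.5 requires clinically significant ECG abnormalities to be followed until they stabilize or return to baseline.

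Much of this stands. Restart is an inference, immediate protection is the same under either section, and Sponsor controls apply. It does not close the gap, because a hold defined by the duration of a work-up has a natural end, whereas a mandatory discontinuation has none. A reasonable site could read it as temporary.

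A reader might infer more than the documents support:

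- **That a site may restart alone, or that both courses comply.** Section 7.1.1.8 requires the Sponsor's involvement, and a restart would breach 5.8.
- **That there is no firm stop at 500 msec.** Section 5.8 states it without condition. Its absence from 7.1.2.5 is an omission.
- **That the step above 30 msec is open-ended.** The step above 60 msec follows it.
- **That the symptomatic paragraph overrides 5.8.** It does not claim to. It sets a work-up at a lower threshold.

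**Conclusion.** The inconsistency is real and limited. For a QTc change above 60 msec, one section requires discontinuation and the other describes a hold whose end is not defined. The open question is whether a child may be re-exposed afterwards, not whether drug is stopped.

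It bears on every change above 60 msec. The number of subjects cannot be estimated, since the documents give no QTc event rate. The remaining enrollment, at least 36 subjects, is at the highest dose, 6 mg/kg. No effect on the primary PK analysis is claimed.

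The conclusion assumes that interruption carries the meaning given in Section 7.1.1.8, and that no site guidance outside these documents settles the matter. It should be fixed because the rule is a pediatric cardiac stopping rule and the change is small.

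**What to change.** Amend Section 7.1.2.5 only:

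1. State that a QTc change from Baseline above 60 msec, or a QTc of 500 msec or more, requires discontinuation of study drug under Section 5.8, and that evaluation and treatment of other causes continue after the stop.
2. State that the two paragraphs leaving discontinuation to judgment (change above 30 msec; symptomatic QTc above 450 or 470 msec) apply only when neither 5.8 criterion is met, that is, change of 60 msec or less and QTc below 500 msec.

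Leave Section 5.8 as it is. Requiring confirmation of the finding there would make an unconditional stop conditional on an undefined step. It could also add an ECG: an asymptomatic subject reaching 500 msec with a change of 30 msec or less (baseline at least 500 − 30 = 470 msec) has no repeat ECG called for now.

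The cost is wording in one section, with no added procedures. Subjects whose change above 60 msec has a reversible cause lose further dosing. Section 5.8 already imposes that loss; how many subjects it affects is unknown.
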